### **1.2.** Participants

The sample size was calculated using G\*power software Version 3.0.10. Data from Tambekar et al. (2016) was used (effect size 0.82,  $\alpha = 0.05$ , power= 0.95). The calculation resulted in a total of 51 participants. Lumbosacral radiculopathy patients with dominant peripheral sensitization of unilateral leg pain were recruited. The patient was diagnosed with peripheral sensitization if they fulfilled the criteria suggested by Schäfer et al. (2009) which included: S-LANSS score < 12, negative sensory and motor examination, and positive neural tissue provocation tests (straight leg raising test, slump test). The inclusion criteria were: adult, pain duration of more than 3 months, patients were diagnosed with peripheral sensitization. Patients with one or more of following criteria were excluded from this study: S-LANSS score  $\geq 12$ , motor or sensory deficits, history of back or lower extremity surgeries, bilateral referred pain, patients with TENS contraindications as described in Jones and Johnson (2009) such as pacemakers and cardiovascular problems, epilepsy, active malignancy, dermatological conditions, and diminished pain sensation.

At SFH, KFHU and DMC outpatients' clinics, the physician referred patients diagnosed with lumbar radiculopathy or lumbosacral radiculopathy with negative dermatomes, myotomes and reflexes examinations finding to the primary investigator. In the initial appointment, the primary investigator explained to each participant the aims and the general procedures of the study. If agreed to participate, the patient signed the consent form (Appendix B, C). The independent examiner started the examination for eligibility with S-LANSS assessment (Appendix D) and an examination of SLR and slump tests. If eligible, the patient was assigned alternatively to one of the three study groups: tensioner group (T- group), slider group (S- group), or control group (C- group). Patients were blinded to the intervention details until they were assigned to one of the study groups. In the alteration type of allocation of groups allocation, the first patient was assigned to slider group, the second was assigned to the tensioner and the third to control group. This order continued even if there was any withdraw until we reached the end of the list then we started filling the gaps in the list from the top with new participants.

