### 1.3.1. Pain intensity

Visual analog scale (VAS) was used to measure pain intensity. It consisted of a 10-cm horizontal line with 'No pain" at one end and "Worst imaginable pain" at the other end. The patient was asked to mark his current leg pain level on the line. The Minimal clinically important difference (MCID) for VAS was reported to be 1.8 - 1.9 cm (Hägg et al., 2003). VAS is a valid and reliable measurement of pain intensity (Ferreira-Valente et al., 2011).

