## **1.4. Interventions**

Each patient received therapeutic sessions over 2 weeks (3 sessions/ week). All patients in all groups received Transcutaneous Electric Nerve Stimulation (TENS). In addition, T-group received tensioner neural mobilization technique and S-group received slider neural mobilization technique.

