### **1.5. Statistical analysis**

SPSS software (version 23, IBM Corporation, New York) was used for statistical analysis. Descriptive data of mean and standard deviation was obtained for all data. The baseline between groups' comparisons on clinical and demographic variables (BMI, age, and VAS) was performed using one-way analysis of variance (ANOVA). A two-way mixed design ANOVA (MANOVA) with post-hoc (Bonferonni Correction) was used to calculate the differences in outcomes measurements with TIME (baseline, 1st, 3rd, and 6th session) as a within-groups factor and GROUP (control, slider, and tensioner) as a between-group factor. The effect size was also calculated with Cohen's *d* to estimate the magnitude of differences within and between groups [small (d = 0.2), medium (d = 0.5), and large (d = 0.8)]. Pearson's correlation was performed to assess the relationship between pains, hip flexion ROM in SLR, knee flexion ROM in slump. The significant level was set at P < 0. 05.

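### Section 1.5 uses the same Cohen's d labels within and between groups, so change shared with TENS-only controls can be called 'large', and the labels need not agree with the quoted VAS MCID

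*Combined protocol and SAP*

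**What the plan says.** The main analysis in section 1.5 is a mixed ANOVA with time and group as factors: "A two-way mixed design ANOVA (MANOVA) with post-hoc (Bonferonni Correction) was used to calculate the differences in outcomes measurements". Means and standard deviations are also planned: "Descriptive data of mean and standard deviation was obtained for all data". Cohen's d is then added "to estimate the magnitude of differences within and between groups [small (d = 0.2), medium (d = 0.5), and large (d = 0.8"). These three benchmarks are the only guide to magnitude in that section, and they apply equally to change within an arm and to differences between arms.

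Two other sections bear on how such labels would be read. Section 1.3.1 gives a reference value for pain: "The Minimal clinically important difference (MCID) for VAS was reported to be 1.8 - 1.9 cm". Section 1.5 does not return to it. Section 1.4 states: "All patients in all groups received Transcutaneous Electric Nerve Stimulation (TENS"). The control arm is therefore TENS alone, and the other two arms are TENS plus one technique.

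Section 1.5 does not name the time-by-group interaction or a between-group contrast as the test of benefit. It does not call within-group d descriptive, does not say which SD enters d, and plans no confidence interval.

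**The concern.** The design can show what a slider or tensioner technique adds to TENS. Only a comparison between arms answers that. A within-group d measures everything that happened to an arm over two weeks, including whatever TENS and the passage of time produced. If it carries the same 'large' label as a between-group d, a report could describe a technique as having a large effect when the controls changed just as much.

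For pain there is a second difficulty. Cohen's d is in SD units and the quoted MCID is in centimetres. The two agree only at particular values of the SD, and the plan does not say how they are to be read together. A difference could be called large yet fall short of the MCID, or reach the MCID and be called medium.

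**Working it through.** **Inputs from the documents.** Labels of 0.2, 0.5 and 0.8 for d (section 1.5); VAS MCID of 1.8 to 1.9 cm (section 1.3.1); a VAS of 10 cm, "It consisted of a 10-cm horizontal line" (section 1.3.1); TENS in all arms (section 1.4).

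**Assumptions.** The VAS SD is not stated, so 1.5 to 3.0 cm is shown. The three label values are treated as lower limits of their categories. The check needs no sample size, and the plan gives no figure of its own on this point to reproduce.

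**Step 1: change shared by all arms.** Suppose VAS falls by 2.0 cm in every arm, with SD 2.0 cm.

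- Within-group d on the raw SD = change / SD = 2.0 / 2.0 = 1.00 in each arm, including control.
- Within-group d on the SD of change = change / (SD × √(2(1 − r))), where r is the correlation between the two occasions. For r = 0.3, 0.5 and 0.7 this is 0.85, 1.00 and 1.29.
- Between-group d = (2.0 − 2.0) / 2.0 = 0.

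Every within-group version exceeds 0.8 although the techniques add nothing. The result depends on the size of the shared change. On the raw SD, 'large' needs a fall of at least 0.8 × 2.0 = 1.6 cm. A shared fall of 1.5 cm gives 1.5 / 2.0 = 0.75, and a fall of 1.0 cm gives 0.50; both are 'medium'.

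**Step 2: labels against the MCID.** The VAS difference at d = 0.8 is 0.8 × SD. The d that corresponds to the MCID is MCID / SD.

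| Assumed SD (cm) | Difference at d = 0.8 (cm) | d at 1.8 cm | d at 1.9 cm |
|---|---|---|---|
| 1.5 | 1.20 | 1.20 | 1.27 |
| 2.0 | 1.60 | 0.90 | 0.95 |
| 2.25 | 1.80 | 0.80 | 0.84 |
| 2.375 | 1.90 | 0.76 | 0.80 |
| 2.5 | 2.00 | 0.72 | 0.76 |
| 3.0 | 2.40 | 0.60 | 0.63 |

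The two scales meet at SD = 1.8 / 0.8 = 2.25 cm or 1.9 / 0.8 = 2.375 cm. Below 2.25 cm, 'large' starts short of the MCID; at SD 2.0 cm the shortfall is 1.8 − 1.6 = 0.2 cm to 1.9 − 1.6 = 0.3 cm. Above 2.375 cm the mismatch reverses: at SD 2.5 to 3.0 cm an MCID-sized difference has d of 0.60 to 0.76, which is 'medium'.

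**The case against.** The strongest reply is that d is only a supplement. The planned ANOVA has a between-group factor and Bonferroni post-hoc tests, means and SDs are reported, and a between-group d is calculated as well. If all arms improved alike, the control arm would show the same within-group d, and a between-group d near zero would stand beside it. That is a fair description. A reader might infer that the plan judges efficacy by d alone, or will take a within-group d as proof of benefit. The documents say neither. What remains is that nothing in section 1.5 ranks the two kinds of d or limits the within-group one to description.

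A reader might also infer that within-group d is bound to look sizeable in every arm, through regression to the mean. The documents give no expected change, and section 1.2 sets no minimum VAS for entry, so for pain this cannot be derived.

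On the MCID, it is tempting to say that 'large' will fall below a threshold the plan itself treats as the least that matters. That goes too far in two ways. The direction of the mismatch depends on an SD the documents do not give. Section 1.3.1 also only reports the MCID; it does not say whether the value refers to change in an individual or to a difference between group means, and it does not make it a criterion.

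**Conclusion.** The point stands as a weakness in how effects are to be described; it is not an error in the planned test. Within-group d cannot isolate the added technique when all arms receive TENS. In the illustration it reaches 1.0 in each arm with a between-group d of 0. That rests on an assumed shared fall of 2.0 cm and SD of 2.0 cm; smaller shared changes would earn a lower label but would be just as uninformative about the technique.

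The labels and the quoted MCID coincide only for an SD of about 2.25 to 2.375 cm. Below that range 'large' can miss the MCID, and above it an MCID-sized difference is called 'medium'. Which case applies cannot be settled from the documents. Because the meaning of the MCID is not specified, the comparison guides relevance and is not a strict test. The importance is modest, since the between-group analysis is already planned and the remedy uses data already scheduled for collection.

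**What to change.** Add to section 1.5, in substance: *For each outcome, the baseline-adjusted between-group mean difference at session 6 will be estimated by ANCOVA and reported in cm or degrees, with Bonferroni-adjusted confidence intervals for the three pairwise contrasts. Conclusions about the added techniques rest on these estimates. The VAS difference will be discussed with reference to 1.8 to 1.9 cm as a guide to relevance, not as a pass/fail rule. Cohen's d will be given for between-group contrasts only, with the SD used stated. Within-group changes will be shown as means and SDs, without effect-size labels.*

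The cost is one model per outcome beyond the mixed ANOVA, which treats baseline as a level of time and so does not supply the adjusted difference directly. Session 6 becomes the focal time point, which the plan does not now specify. Results may also look less favourable than labelled within-group effects would. No new measurements are needed. The plan is written in the past tense, so if results have already been seen, the addition should be identified as made afterwards.
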